#### Secondary objective 1:

We estimate needing 28 participants. This accounts for an anticipated effect size in the outcome (VAS score) of 0.35, with one predictor (cough frequency registered by Hyfe), and accounting for a loss of follow up of 10% of the participants. The significance level is set at 0.05, with a statistical power of 80%.

#### Secondary objective 2:

We aim to include all participants with an etiologic diagnosis of cough into the annotated datasets, so no specific sample size is required for completion of this objective.

#### Secondary objective 3:

We aim to determine the sensitivity and specificity of Hyfe to detect and classify coughs appropriately. For this objective, all coughs will be voluntary, so the cough prevalence of coughs in our sample will be 100%. Including a minimum of 24 patients with 12 voluntary coughs each (288 coughs in total) will be required to achieve a power of 90% at 5% significance level to detect a difference of 5% in the value of sensitivity from 95% in the human observer to 90% by Hyfe. This minimum sample size is also sufficient to detect with 70% power a difference in specificity of 10% from 90% in the human observer to 80% in Hyfe at 5% significance. (Bujang and Adnan, 2016).

#### Secondary objective 4

Given the similarity with secondary objective 3, the same sample size calculation method was used. Twenty-four participants (12 males and 12 females, preferentially from different age groups) will be recruited for this exploratory analysis.

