### **7.2. Efficacy variables**

For the primary objective 1, efficacy will be measured by determining Hyfe's capacity to predict a diagnosis, or reflect clinical evolution of patients, based on cough signatures. For this, the acoustic characteristics of coughs (mean frequency, volume, amplitude) registered from participants with an etiologic diagnosis, will be described, to identify patterns associated to specific conditions. Additionally, the Area Under the Curve, sensitivity, and specificity of the AI system will be retrospectively evaluated with the annotated cough registries.

For the secondary objective 1, the efficacy variable will be the daily score in the online VAS, and the coughs per recorded hour.

For the secondary objective 2, there is no clear efficacy variable. We will retrospectively include anonymous coughs registered in patients with an etiologic diagnosis and annotated with data in online datasets from where they can be used to train this and similar AI systems in the future.

For the secondary objectives 3 and 4, efficacy variables will include the calculated sensitivity, specificity, positive predictive value (PPV), and negative predictive value (NPV) of Hyfe, compared to two trained human observers.

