The validation parameters for the application will be calculated in the following way: Sensitivity = True positives (TP)/True positives (TP) + False negatives (FN), Specificity = True negatives (TN)/True negatives (TN)+ False positives (FP). PPV= TP/TP+FP, NPV= TN/TN+FN.

Any sound identified as a cough by both human observers will be considered a positive result for cough. TP will be defined as those sounds identified as a cough by Hyfe, and both human observers. Similarly, a sound identified as non-cough by both observers will be considered a negative. TN will be defined as those sounds not recorded as coughs by neither Hyfe, nor any human observer. Sounds identified as coughs by Hyfe, but not by both human observers will be considered FP, and those identified as non-cough by Hyfe, but not by both human observers will be classified as FN. Sounds for which no consensus is reached by both human observers will be excluded from the analysis. Time stamps from each individual sound will be used to identify them, and determine which ones were not picked up by Hyfe's detection algorithm.

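### Objective 3's 70% specificity power cannot be reproduced from the plan, which sets no number of non-cough sounds; its 90% sensitivity power holds only for 288 independent coughs against a fixed benchmark

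*Combined protocol and SAP*

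**What the plan says.** Section 9.2, secondary objective 3, gives one count of sounds: "Including a minimum of 24 patients with 12 voluntary coughs each (288 coughs in total) will be required to achieve a power of 90" per cent, for a fall in sensitivity "from 95% in the human observer to 90% by Hyfe". It describes the sample as all voluntary coughs, "so the cough prevalence of coughs in our sample will be 100" per cent. The next claim is "This minimum sample size is also sufficient to detect with 70% power a difference in specificity of 10" percentage points, from 90% to 80%, also at 5% significance. The calculation is attributed to a cited sample-size paper. Sidedness, and whether the comparison is one-sample or two-sample, are not stated.

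Section 9.1 defines "Specificity = True negatives (TN)/True negatives (TN)+ False positives (FP"), that is TN/(TN+FP), counted sound by sound: "Time stamps from each individual sound will be used to identify them". It adds "Sounds for which no consensus is reached by both human observers will be excluded from the analysis". It names no interval method, no test and no allowance for repeated sounds from one person.

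Section 4.1 (validation of technical performance) has participants read, count and sneeze as well as cough, but gives no number for any of these. Section 7.2 says that for objectives 3 and 4 "efficacy variables will include the calculated sensitivity, specificity, positive predictive value (PPV), and negative predictive value (NPV) of Hyfe". Section 9.2 reuses the objective 3 method for objective 4, where recording runs for 6 to 24 hours. That analysis is labelled exploratory and carries no power figure.

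**The concern.** The denominator of specificity is the number of non-coughs. The plan's only count is of coughs, at a stated prevalence that leaves no non-coughs. Section 4.1 contradicts that prevalence but supplies no replacement number. A reader therefore cannot tell whether 70% describes this design. The same open number sets the mix of coughs and non-coughs, and so drives PPV and NPV, two of the four listed efficacy variables.

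The sensitivity figure has a different weakness. The 288 coughs come 12 each from 24 people. If Hyfe's accuracy varies between people, the coughs carry less information than 288 independent ones. Power is then below the stated value, and an interval that pools all sounds is too narrow.

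**Working it through.** **Inputs.** From 9.2: 24 × 12 = 288 coughs; sensitivity 95% against 90%; specificity 90% against 80%; 5% significance, taken as two-sided unless noted. From 9.1: specificity = TN/(TN+FP). Not in the documents: the number of non-coughs, and the intra-participant correlation (ICC). The ICC values below are assumptions.

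**1. Reproducing the 90%.** One-sample normal formula: power = Φ[(|p0−p1|√n − 1.96√(p0q0)) / √(p1q1)]. With n = 288, p0 = 0.95, p1 = 0.90: (0.05 × 16.97 − 1.96 × 0.218)/0.30 = 1.40, power 92.0%. The exact binomial test gives 89.5%. So the 90% is reproduced as a one-sample comparison with a fixed 95%.

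Read as two independent samples of 288, power = Φ[(|p0−p1|√n − 1.96√(2p̄q̄)) / √(p0q0+p1q1)] = Φ[(0.8485 − 1.96 × 0.3725)/0.3708] = Φ(0.32), about 62.5%. On that reading the 90% does not hold.

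**2. Trying to reproduce the 70%.** At 100% cough prevalence TN+FP = 0 and power is undefined. Other counts that might be inferred:

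- 288 non-coughs, one-sample: (0.10 × 16.97 − 1.96 × 0.30)/0.40 = 2.77, power 99.7% (also 99.7% exact).
- 288 per group, two independent samples: (1.697 − 1.96 × 0.505)/0.50 = 1.41, power 92%.
- 24 non-coughs, one per person: 16% to 50% by the one-sample normal formula, depending on sidedness and on which rate is the null.
- 144 per group, two samples: 66% two-sided, 77% one-sided.

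None falls within 2 points of 70%.

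**3. What 70% would need, if sounds were independent.** One-sample normal: ((1.96 × 0.3 + 0.524 × 0.4)/0.1)² = 63.6, or ((1.96 × 0.4 + 0.524 × 0.3)/0.1)² = 88.6 with 80% as the null. The exact test gives 78 to 94. The one-sample range is thus 64 to 94, or 64/24 = 2.7 to 94/24 = 3.9 per person. Two samples need 120 (one-sided) to 157 (two-sided) per group. The plan states none of these counts.

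**4. PPV and NPV.** Take 12 coughs and k non-coughs per person, sensitivity 90%, specificity 80%. Then PPV = 10.8/(10.8 + 0.2k) and NPV = 0.8k/(0.8k + 1.2).

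| k | PPV | NPV |
|---|---|---|
| 3 | 95% | 67% |
| 12 | 82% | 89% |
| 48 | 53% | 97% |

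**5. Clustering.** The design effect is 1 + 11 × ICC, and the effective number of coughs is 288 divided by it, rounded down. Power was simulated for a leave-one-participant-out jackknife interval on the logit scale, with t on 23 degrees of freedom (beta-binomial data, 24 people × 12 coughs, 60,000 replicates, true 90% against 95%).

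| Assumed ICC | Effective coughs | Simulated sensitivity power |
|---|---|---|
| 0 | 288 | 90% |
| 0.01 | 259 | 87% |
| 0.05 | 185 | 76% |
| 0.10 | 137 | 64% |
| 0.20 | 90 | 46% |

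A nominal 95% exact interval that ignores clustering covers a true 90% in about 90%, 85% and 75% of samples at ICC 0.05, 0.10 and 0.20.

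**6. The observer figures.** If sounds without consensus are excluded, both observers match the reference on every analysed sound. Their 95% and 90% are then not estimated and can only act as fixed benchmarks. However, the FP and FN definitions in 9.1, read literally, also take in sounds on which the observers split, which conflicts with the exclusion. The benchmark reading depends on the exclusion governing.

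**The case against.** The 70% may come from the cited sample-size paper, which is not available here. The 100% clause may be loose wording for the fact that every cough is voluntary. Non-cough sounds will be recorded, and on the one-sample reading 3 to 4 independent ones per person already give 70%; a session of about 30 minutes plausibly yields more. The objective is secondary, it asks to determine accuracy, and 9.1 sets no test or threshold. Objective 4 claims no power at all.

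Most of this stands, and it limits the point. It does not supply the missing count: the plan guarantees no number, and either reading of the 100% clause leaves the denominator unset.

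The clustering loss is also hypothetical, since the documents give no ICC. Its size depends on the method as well: at ICC 0.20 power is 41% by the exact test at the effective sample size, 46% by the simulated jackknife and 56% by the normal formula.

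A reader might infer that specificity cannot be estimated, that its true power is below 70%, or that 24 participants are too few. The documents support none of these. Section 4.1 provides non-cough sounds, the power could lie well above 70%, and no ICC is given from which to judge the sample inadequate.

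**Conclusion.** The point holds as one of reproducibility and unstated assumptions, and should be fixed. The 70% follows from no count in the plan, and this conclusion needs no assumption about the ICC. The 90% is sound for 288 independent coughs in a one-sample comparison with a fixed 95%, and the plan states neither condition. How far power falls below 90% depends on an ICC that has to be assumed. The consequence is confined to planning figures, to the width of any pooled interval, and to the interpretation of PPV and NPV.

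**What to change.** 1. In 9.2, delete the 100% prevalence clause. State the planned minimum number of analysed, time-stamped non-cough sounds per participant. Either build the script from discrete sounds or give a rule for segmenting reading and counting, because one such prompt is not one analysed sound.
2. Delete the 70% or re-derive it from that count. State that both powers are one-sample, two-sided 5% comparisons with fixed benchmarks, that the 90% assumes independent sounds, and what it becomes over an assumed ICC range. For scale only: with exactly 12 analysed non-coughs per person, simulated specificity power by the same method is 99.7%, 99%, 97%, 92% and 78% at ICC 0, 0.01, 0.05, 0.10 and 0.20.
3. In 9.1, report sensitivity and specificity for objectives 3 and 4 with a 95% interval that allows for clustering by participant; the jackknife above is one option. Report PPV and NPV together with the share of coughs among analysed sounds.
4. In 9.1, make the FP and FN definitions agree with the exclusion of sounds without consensus.
5. For objective 4, delete the sentence reusing the objective 3 calculation, since 6 to 24 hours of free recording has no fixed cough count. Keep the exploratory label.

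The cost is wording in 9.1 and 9.2 and a minimum number of non-cough sounds in the existing on-screen script, best set before sessions are recorded. No participants or visits are added. The downside is that the stated sensitivity power looks less favourable once an ICC above 0 is assumed; the change discloses that loss and does not remove it.

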### **Validation of Hyfe's technical performance**

A subgroup of participants and/or a group recruited outside the clinical setting will provide consent to participate in this sub-study by marking the sub-study box in the consent form.

Participants will remain for approximately 30 minutes in a quiet room. A smartphone connected to a lapel microphone will be placed at approximately 50 cm from the participant's mouth, another smartphone of the same model, not connected to an external microphone will be placed next to the first one. Each participant will also wear a lapel microphone connected to an audio recorder.

Participants will be instructed via a computer monitor to generate a series of voluntary sounds including but not limited to: reading a text, coughing, counting, sneezing and similar common sounds. There will be silent pauses between the elicited sounds. All sounds throughout this period will be recorded. Any accidental conversation will be deleted. The final audio will be stored in a database, coded with the participant's ID, sex, and age.

The cough counts registered by the two smartphones will be compared to the consensus evaluation of two medically trained researchers, who will be instructed to determine whether individual sounds were coughs or not.

Finally, the experiment will be repeated, playing back the records obtained from participants using a desktop speaker located at 50 cm of the two smartphones, to compare the application's performance detecting live vs recorded coughs. Audio will be played at decibels matching the average intensity of human coughs (Doherty et al, 1997).

A second sub-group of at least 24 participants will be instructed to use Hyfe continuously for a period between 6 and 24 hours, while they record themselves using a MP3 recorder connected to a lapel microphone. For this, participants will be provided with a smartphone exclusively destined to run Hyfe Cough Tracker, while simultaneously wearing the Hyfe Air wearable system. MP3 records will be processed and manually reviewed by two specially trained healthcare providers to count the number of coughs recorded. This data will be used to evaluate the performance of both devices compared to human listeners in a real-life scenario.

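### Secondary objective 3 is powered against a human observer with 95% sensitivity, but the analysis makes the observers the reference standard, so that comparison is not in the design

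*Combined protocol and SAP*

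**What the plan says.** **Sizing (section 9.2, secondary objective 3).** The sample is at least 24 people giving 12 coughs apiece, 288 overall, with power put at 90% and the significance level at 5%. The target of that power is worded as "to detect a difference of 5% in the value of sensitivity from 95% in the human observer to 90% by Hyfe". For specificity, the plan says that the same sample can "detect with 70% power a difference in specificity of 10% from 90% in the human observer to 80% in Hyfe". Cough prevalence is put at 100% because all coughs are voluntary. The section does not give a number of non-cough sounds or say whether the tests are one- or two-sided. Secondary objective 4 adopts the same calculation.

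**Analysis (section 9.1, secondary objectives 3 and 4).** "Any sound identified as a cough by both human observers will be considered a positive result for cough". A non-cough is defined in the same way, by both observers agreeing. "Sounds for which no consensus is reached by both human observers will be excluded from the analysis". Formulas follow for the sensitivity, specificity, PPV and NPV of Hyfe. There is no formula for an observer's accuracy, no benchmark value and no hypothesis test.

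**Procedures and endpoints.** Section 4.1 (validation of technical performance) compares the smartphones' counts with the consensus of two medically trained researchers. Section 7.2 lists Hyfe's accuracy measures, judged against two trained observers. Both agree with 9.1 that the observers are the reference.

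**The concern.** A power statement should describe a comparison that the analysis will make. Here the sizing text treats the human observer as a second diagnostic method with its own error rate (95% sensitivity, 90% specificity), while the analysis treats the two observers as the truth. A method cannot be both on the same sounds.

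What is at stake is the meaning of the 90%. A reader of the final report would take it that the study had 90% power to show a difference between people and Hyfe. The planned data contain no human rate with which to make that comparison. Unless 95% is declared as a fixed benchmark, or the aim is declared as estimation, someone will have to choose after the fact what Hyfe's observed sensitivity is to be judged against.

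**Working it through.** **Inputs, all from section 9.2 unless noted.** Sensitivity 95% and 90%. Specificity 90% and 80%. n = 24 × 12 = 288 coughs. Significance level 5%, taken as two-sided because the plan does not say. Coughs are treated as independent, as the plan's own calculation appears to do. The cited sample-size source was not available.

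**1. What the reference definition implies.** Every analysed sound is one on which both observers gave the same label, and that label is the truth (section 9.1). Each observer's label therefore equals the truth on every analysed sound, so an observer has no false negatives and no false positives. Sensitivity and specificity are exactly 100% for both, and 95% or 90% cannot arise.

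**2. Reproducing the stated 90%.** For a one-sample test of Hyfe against a fixed p0 = 0.95 when the truth is p1 = 0.90:

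power = Φ{[|p1 − p0|√n − 1.96√(p0(1 − p0))] / √(p1(1 − p1))}

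= Φ{[0.05 × 16.971 − 1.96 × 0.2179] / 0.3} = Φ(1.40) = 92.0%.

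The exact binomial version rejects in the lower tail at 265 or fewer detected coughs and has 89.5% power. The smallest n with exact power of 90% is 279. That is 11.6 coughs per participant over 24 participants, which rounds up to 12 and gives 288. One-sided, power at 288 would be 94.9% (normal) or 92.9% (exact). The stated figure therefore reproduces well as a test against a constant.

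**3. The comparison as worded.** For two independently measured sensitivities with 288 coughs per method:

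power = Φ{[0.05 × 16.971 − 1.96√(2 × 0.925 × 0.075)] / √(0.95 × 0.05 + 0.90 × 0.10)} = Φ(0.32) = 62.5%.

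Reaching 90% would take 582 coughs per method. If observer and Hyfe were scored on the same coughs against some third truth, power would depend on the share of coughs on which they differ, which the plan does not give. Over an assumed 5% to 14%, McNemar power at 288 runs from 97% down to 62%. An assumed 7% would give Φ{[0.8485 − 1.96√0.07] / √(0.07 − 0.0025)} = Φ(1.27), about 90%. So a paired reading can be made to fit, but only with an input and a truth standard that the plan does not supply.

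**4. Precision on the planned data.** At 90% sensitivity, the half-width of the 95% interval is 1.96√(0.9 × 0.1/288) = 3.5 points. With 12 coughs per participant the design effect is 1 + 11 × ICC. At assumed ICCs of 0.05 and 0.30 the half-width becomes 4.3 and 7.2 points.

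**5. Reverse direction, for illustration.** Power to exclude 90% when the true sensitivity is 95%: Φ{[0.8485 − 1.96 × 0.3] / 0.2179} = Φ(1.20) = 88.4% (normal), or 86.5% exact.

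**6. Specificity.** One-sample, 90% against 80%, with 288 sounds: Φ{[0.10 × 16.971 − 1.96 × 0.3] / 0.4} = Φ(2.77) = 99.7%, not 70%. Power of 70% corresponds to roughly 50 to 78 non-cough sounds, depending on sidedness and on exact or normal calculation. The plan gives no such count, and its 100% prevalence statement leaves no non-coughs in the sample being sized.

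**The case against.** The strongest reply is that this is a mislabelled null value and little else. If 95% is read as a fixed standard of good performance, loosely described as the human level, the arithmetic holds, 288 is right, and the test can be run on the planned data with observer agreement as truth. The objective is also worded as determining sensitivity and specificity, which is estimation, and the estimators in section 9.1 are unaffected. All of this stands, and it limits the point to the wording of 9.2 and the absence of a matching analysis in 9.1.

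Three stronger readings are tempting, and the documents do not support them.

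- A reader might infer that the objective cannot be tested at all, or that 288 is the wrong number. The one-sample reading shows otherwise on both counts.
- A reader might infer that the study would count a non-significant difference as validation, so that less data makes a pass easier. No section sets a pass/fail rule or plans a test, so this criticises a rule that is not in the plan.
- A reader might infer that the on-screen prompts ("Participants will be instructed via a computer monitor to generate a series of voluntary sounds", section 4.1) already provide a truth standard independent of the observers. The protocol does not describe a time-stamped prompt log, one sound per prompt or a compliance check. A prompt records what was asked for, not what was produced.

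**Conclusion.** The inconsistency is real. Section 9.2 attaches 90% power to a fall "from 95% in the human observer to 90% by Hyfe", and sections 4.1, 7.2 and 9.1 leave no observer rate to compare with, because observer accuracy is 100% by definition. The same holds for the 90% observer specificity.

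For sensitivity, the consequence is that the stated power belongs to an unplanned one-sample test against a fixed 95%. The plan's number of coughs survives. For specificity there is also a numerical gap: 70% power does not follow from 288 sounds.

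These figures assume a two-sided 5% test and independent coughs. Clustering within participants would lower the power and widen the intervals, by an amount the documents do not allow one to fix. The contradiction itself rests on no assumption. This should be corrected, but it affects one secondary objective (and objective 4, which borrows the calculation), not the primary objective.

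**What to change.** In section 9.2, remove the human observer as comparator for sensitivity and choose one of two restatements:

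- **Benchmark.** Declare 95% a fixed performance value, state the sidedness, and add the matching one-sample test to section 9.1. Power with 288 independent coughs is about 90% at a true 90%.
- **Precision.** Since the aim is to determine accuracy, state the expected 95% interval: about ±3.5 points at 90% sensitivity with 288 coughs, before allowing for clustering within participants.

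If the sponsor would rather show that sensitivity exceeds a minimum, it should specify that minimum before analysis. As an illustration only, requiring the lower 95% limit to lie above 90% has about 86% to 88% power at a true 95%. The plan uses 90% as Hyfe's assumed value, not as an acceptance limit, so that threshold would be a new decision.

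For specificity, remove the human comparator in the same way, state how many non-cough sounds the figure rests on, and recompute the power or precision from that number. Carry the wording over to secondary objective 4. If a true human-versus-Hyfe comparison is wanted, the plan must first name a truth standard independent of the observers and then size a paired analysis.

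The cost is wording in 9.2 and, for the benchmark option, one added test in 9.1. Recruitment and the section 9.1 estimators stay as they are, unless the paired comparison is chosen. The change should be made before the data are analysed, so that the benchmark is not chosen with results in view.
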